4.1 RANDOMISATION PRACTICALITIES

Further details on the generation of randomisation lists can be found in [Section 9.1](#).

Randomisation will be performed online. To randomise a child the information contained on a completed randomisation CRF\worksheet will be entered into the online trial database accessible from the local clinical sites that will automatically check for eligibility. Only children with completed

and verified randomisation CRFs\worksheets on the database will be able to be randomised. The computer-generated sequentially numbered randomisation lists will be securely incorporated within this online trial database, and allocation concealed until the point of the next randomisation. Allocation will be made after eligibility has been confirmed by local site staff through the online database. Only the next randomisation will be provided, the remainder of the list will be concealed (ensuring allocation concealment). Delegated member(s) of staff at each site, not directly involved in patient care, will be responsible for carrying out the randomisation process restricted using role-based access. The details of the child's treatment allocation and PediCAP Study ID will be notified to clinical staff, and the Study ID and allocation cross checked between those randomising and those managing the child clinically.

If the site's internet connection is unavailable at the time of randomisation, the child's details can be provided to staff at the CTU by email or phone. At the CTU, staff will verify eligibility and perform the randomisation using the online system. The details of the child's treatment allocation and PediCAP Study ID will be notified to the trial team at the site by email or phone within one hour of the receipt of the randomisation form (during normal working hours).

If the main electronic randomisation system is not working, randomisations will not take place, and this should be recorded as the reason that the child was not randomised.

The child's Study ID and the date of randomisation will be entered into the trial register at the site.

The trial is open-label so there is no need for unblinding.

4.2 CO-ENROLMENT GUIDELINES AND REPORTING

Concurrent participation in any other clinical study of an investigational medicinal product is not allowed for the duration of the follow-up period, i.e. within 28 days after randomisation. Participation in observational studies is acceptable in accordance with local guidelines.

5 TREATMENT OF CHILDREN

5.1 INTRODUCTION

All children will initiate treatment with intravenous antibiotics as per the relevant site's standard of care (within the regimens listed in [Section 5.2.1](#) below) and the eligibility criteria.

In the main trial (PediCAP-A), children will effectively firstly be randomised 5:5:1 to either oral step-down amoxicillin (amoxicillin group); oral step-down co-amoxiclav (co-amoxiclav group); or to remain on intravenous antibiotics (IV group).

Within the amoxicillin and co-amoxiclav groups, children will simultaneously be further randomised 1:1:1:1 to receive 4, 5, 6, 7 or 8 days of total antibiotic treatment (from the start of intravenous antibiotic therapy).

Children randomised to the IV group will receive 5 days of treatment with one of the PediCAP standard of care IV antibiotic regimens (see [Section 3.1](#)). Thus, each child in the main trial will be randomised to one of 11 different groups.

In the Phase II PK trial (PediCAP-B), a separate group of children will be randomised 1:1 to oral step-down with co-amoxiclav 4:1 vs 14:1 (1:1 randomisation ratio) for a total duration of 6 days antibiotics from the start of intravenous antibiotics. Children will be approached for recruitment to either PediCAP-A or PediCAP-B, not both.

Oral treatment will commence when the child is judged well enough to take oral antibiotics, which will be given with food where possible. See [Section Error! Reference source not found.](#) below for details.

Treatment will be open-label without blinding and will be dispensed at the point of oral step-down for the amoxicillin and co-amoxiclav groups, for the duration needed to complete the randomised total antibiotic course (starting at the time intravenous antibiotics were administered, excluding any antibiotics taking in the community prior to admission). For example:

- A child randomised to total 8 days antibiotics who is well enough to start taking oral antibiotics after 3 days of intravenous antibiotics will receive 5 days oral antibiotics
- A child who is randomised to total 4 days antibiotics who is well enough to start taking oral antibiotics after 2 days of intravenous antibiotics will receive 2 days oral antibiotics

5.2 INTRAVENOUS ANTIBIOTICS (ALL CHILDREN)

5.2.1 PRODUCTS & TREATMENT SCHEDULE

At the point of randomisation, children should have received no more than 24h of intravenous antibiotics ([Section 3](#)). However, standard-of-care intravenous treatment should be for at least 24 hours for all children, whether randomised to oral step-down or continuous intravenous antibiotics and regardless of what duration of intravenous antibiotics has been received at the point of randomisation. That is, children randomised to step-down to oral antibiotics should not do so before receiving at least 24h of intravenous antibiotics. Those randomised to intravenous antibiotics will be treated with intravenous antibiotics for 5 days in total (from start of intravenous antibiotics, excluding oral/intramuscular antibiotics received in the community). Parents/carers of children randomised to 5 days' IV will receive travel costs for any additional days their child remains in

hospital solely for the purpose of receiving intravenous antibiotics within the trial, since a few of these children might otherwise be discharged early on oral antibiotics depending on local practice (site-specific).

Dosing should follow the local standards of care (summarised in [Table 6](#)) which generally follow WHO recommendations where given ([Table 2](#)). Local standards of care may differ from WHO recommendations due to factors such as local susceptibility patterns, drug availability and institutional prescribing guidelines.

The choice of intravenous antibiotics will be made by the treating physician prior to randomisation. Doses should be given intravenously: if there is a problem with venous access, then isolated post-randomisation doses that should have been given intravenously may be given intramuscularly. Doses will be dispensed from ward stock and prepared and given by the ward nurses. Children will be hospitalised for the entire parenterally administered treatment duration (5 days for those randomised to intravenous antibiotics). After completing their intravenous antibiotics (either after 5 days or after moving to oral-stepdown), children should be discharged as soon as they are clinically stable.

Table 6: Dosing of standard intravenous antibiotics

DRUG	SCHEDULE
Ampicillin	IV/IM: 50 mg/kg every 6 hours
Benzylpenicillin (penicillin G)	IV: 50'000-100'000 U/kg every 6 hours
Cefotaxime	IV: 50 mg/kg every 6 hours or 33.3 mg/kg every 8 hours
Ceftriaxone	IV: 80 mg/kg/d as a single dose once daily OR IV/IM: 50 mg/kg every 12 hours (max single dose 4g) OR IV/IM: 100mg/kg as a single dose once daily
Gentamicin	IV/IM: 5-7.5 mg/kg as a single dose once a daily

Note: IV=intravenous, IM=intramuscular

Following the 2013 WHO Pocketbook of hospital care for children [27], if the child does not show signs of improvement within 48h of starting intravenous antibiotics and staphylococcal pneumonia is suspected, then the child should switch to gentamicin (dosed as in [Table 6](#)) and cloxacillin 50 mg/kg IM or IV every 6h. Cloxacillin can be replaced by another anti-staphylococcal antibiotic, for example oxacillin, flucloxacillin or dicloxacillin.

5.2.2 DOSE MODIFICATIONS, INTERRUPTIONS & DISCONTINUATIONS

The doses of intravenous drugs are as recommended by the WHO pocket book for hospital care 2013 [27] or local standard of care. Intravenous doses may be modified, intervals between doses increased or antibiotics discontinued in the following situations:

- renal failure (all)
- combined renal and liver failure (ceftriaxone)
- therapeutic drug monitoring (gentamicin)

After receiving at least 24h of intravenous antibiotics, children randomised to oral step-down should move to oral antibiotics as soon as they have improved clinically, are currently clinically stable or

continuing to improve and can tolerate oral medication (e.g. without vomiting). See [Section Error! Reference source not found.](#) below.

5.2.2.A Stopping Drug Early

Adverse events caused by drug toxicity (i.e. adverse reactions) leading to a treatment change are expected to be rare, and should be managed following local standard of care. In the situation when a penicillin allergic reaction is suspected (e.g. typical, indicative skin rash) it would be customary to switch to an antibiotic of a different class and follow relevant safety reporting procedures. Children should remain in the study for follow-up and should continue to follow the assessment schedule.

5.2.2.B Inadequate Response or Relapse on Intravenous Treatment or Post-discharge

Non-response to intravenous antibiotics in children randomised to 5 days' intravenous therapy, and subsequent relapse, should be treated as per normal standard of care; example scenarios are provided in [Section 0](#) below.

5.2.3 COMPLIANCE & ADHERENCE

All intravenous doses will be administered by ward nurses and recorded on CRFs\worksheets by study staff. Therefore non-adherence will be minimal.

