1.4.3 RATIONALE FOR INCLUSION OF “BENCHMARKING” CONTINUOUS INTRAVENOUS GROUP

The challenge with antibiotic trials is identifying an appropriate “standard of care”, since current practice is often very variable in terms of both drug and duration, reflecting local opinion as well as local resistance patterns. However, were the trial to only include the durations above, even if we estimate the “duration-response” curve for each of amoxicillin and co-amoxiclav oral step-down, it would be reasonable to ask how these curves related to continuing on intravenous antibiotics for the whole duration of treatment, particularly since WHO guidance currently has variable recommendations for the duration of injectable antibiotics for severe pneumonia ranging from at least 5 to at least 10 days.

We will therefore add an 11th randomised group which will receive **5-day intravenous antibiotics with no oral step-down**. Hospitals participating in PediCAP who undertook a short epidemiological survey identified that more than 50% of children started on intravenous antibiotics for CAP stayed in hospital for at least 4 days or longer (see **Section 1.4.4**). The choice of five days is also in accordance with the minimal WHO recommendation, although clinical practice varies. As standard-of-care is variable, this is not a formal control group, but will enable the trial to “benchmark” the duration-response curve for each oral step-down option.

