1.4.4 SERVICE EVALUATION IN RECRUITING SITES

To inform protocol development, a short service evaluation was conducted in four of the five trial sites (South Africa, Uganda, Zambia and Zimbabwe) in February 2018. Brief details of consecutive children aged 2 months to 10 years admitted for antibiotic treatment of pneumonia were recorded for 2 weeks or 30 children, whichever was achieved first. In total, 93 children were recorded across the sites (12-32 children/site). Of these, 79 (85%, 40/79 males) children were commenced on intravenous antibiotics at admission to hospital. The commonest intravenous regimens were those recommended by the WHO and included in the eligibility criteria below (56/79 – 71% -

benzylpenicillin or ampicillin plus aminoglycoside; 12/79 – 15% - ceftriaxone or equivalent third generation cephalosporin). The modal duration of hospitalisation was 4 days, and 47/79 (59%) children were hospitalised for 4 days or longer. Only 6/79 (8%) children were discharged from hospital without further oral antibiotic treatment, and half of these had been treated in hospital for 7 days or longer already. Further relevant results for the 79 children treated with intravenous antibiotics are summarised in **Table 3** below.

Table 3: Additional details of 79 children treated with intravenous antibiotics in trial sites

VARIABLE	SUMMARY			
Age (in months)	Median	IQR	Min	Max
	12	6-18	3	98
Weight (in kg)	Median	IQR	Min	Max
	7.8	6.6-9.3	2.9	22.2
	Children weighing <4kg n=3			
Underlying disease/risk factor	Malnutrition	HIV exposure	Chronic neurological disease	HIV infection
	13/79 (16%)	7/79 (9%)	6/79 (8%)	3/79 (4%)
Investigations	Chest X-ray obtained		Inflammatory marker measured	
	31/79 (39%)		63/79 (81%)	
Supportive therapies during stay	Supplemental Oxygen	IV fluids	Nasogastric feeds/fluids	
	51/79 (65%)	14/79 (18%)	5/79 (6%)	

Note: IQR=interquartile range.

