9.5 ANALYSIS PLAN (BRIEF)

The analyses will be described in detail in a full Statistical Analysis Plan. This section briefly summarises the main issues.

The primary analysis population is intention-to-treat, including all randomised children, regardless of treatment received. This corresponds to estimating the impact of the effectiveness of the strategies of stepping down to oral amoxicillin vs co-amoxiclav and varying total duration of antibiotics. However, in secondary analyses we will also use inverse-probability weighting methods to adjust for deviation from randomised strategy, both duration of antibiotic treatment and oral-stepdown, which is a more efficient approach than defining a per-protocol population [55].

As follow-up is short (28 days post-randomisation) lost-to-follow-up should be low, and in each population, the primary comparison between randomised groups will be conducted using binomial regression, reported on the risk difference scale (following the sample size calculation which is based on risk differences). The primary analysis will adjust for the randomisation stratification factors (site and the other factorial randomisation). The primary analysis will be conducted on observed data. Secondary analyses will use multiple imputation with chained estimating equations to impute outcomes for the small (5%) number of expected missing outcomes due to losses to follow-up before 28 days post-randomisation (the sample size calculation in [Section 9.3](#) includes an inflation factor to allow for this). Imputation will be done separately within each randomised group to allow for unknown interactions, and will be based on outcomes and main baseline characteristics as recommended. Duration-response curves will be estimated separately for oral amoxicillin and oral co-amoxiclav randomised groups using fractional polynomials to flexibly model the impact of duration on response following Quartagno et al [33]. A combined model will test whether there is evidence that these duration-response curves vary between co-amoxiclav and amoxicillin using main effects and interactions (i.e. subgroup effects), specifically the following key factors:

- site

- severity
- age
- HIV infection and exposure
- malnutrition (assessed by weight-for-height Z-scores, according to the WHO Growth Standards, and pedal oedema/MUAC)

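### Nurse-given doses do not make 5-day IV adherence secure, and early oral switching in the IV group would tilt the ITT-primary non-inferiority comparison towards success

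*Protocol*

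**What the plan says.** The eleventh randomised group in PediCAP-A receives "5-day intravenous antibiotics with no oral step-down" (protocol 1.4.3). On adherence to intravenous treatment, 5.2.3 reasons that ward nurses give every dose and study staff record it, and concludes: "Therefore non-adherence will be minimal". Section 5.2.1 offers travel costs to families in this group for the extra days in hospital, "since a few of these children might otherwise be discharged early on oral antibiotics".

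Section 1.4.4 reports a survey of four of the five sites, covering 79 children started on IV antibiotics: "The modal duration of hospitalisation was 4 days, and 47/79 (59%) children were hospitalised for 4 days or longer". It adds: "Only 6/79 (8%) children were discharged from hospital without further oral antibiotic treatment".

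Section 9.3.1 powers a non-inferiority comparison of co-amoxiclav step-down (500 children) with 5-day IV (100 children), using a 10% margin, and makes no allowance for non-compliance. Section 9.5 states: "The primary analysis population is intention-to-treat, including all randomised children, regardless of treatment received". It gives no separate rule for the non-inferiority comparison. It plans, as secondary analyses, inverse-probability weighting for deviation from the randomised strategy in both duration and oral step-down.

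**The concern.** Nurse administration ensures that a child who is on the ward and still prescribed IV gets the doses. It does not bear on a decision to change a recovering child to oral treatment or to go home before the fifth day. The trial is open-label, and 11.2.2 leaves the clinician free to give alternative treatment at any stage. The conclusion in 5.2.3 therefore does not follow for the kind of non-adherence that matters most in this group.

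The direction of the resulting error also matters. An IV-group child switched early receives something close to what the step-down groups receive. Under ITT this pulls the two failure rates together, and in a non-inferiority comparison that favours success. The Summary of Trial defines the duration hypothesis by thresholds around the 5-day IV regimen, so a diluted IV group would weaken the benchmark as well as the formal test. The group is small: with about 95 evaluable children, 10% switching is only about 10 children.

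**Working it through.** **Inputs.** From 9.3.1: 500 v 100 children, 9% failure in both groups, 10-point margin, two-sided alpha 0.05 (one-sided 0.025). The 5% loss to follow-up is stated there for the drug comparison; applied here it gives 475 v 95. From 1.4.4: 47/79 stayed 4 days or longer. Assumed, because the documents do not give them: the fraction c of the IV group that switches early, and the share h of the excess step-down risk that a switcher takes on.

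**The plan's own power.** With the unpooled normal approximation, power = Φ(0.10/SE − 1.96).
- 500 v 100: SE = √[0.09 × 0.91 × (1/100 + 1/500)] = 0.03135, so power = Φ(1.23) = 89.1%. This reproduces the stated 89%. At 12% failure the result is 80.2%, matching the stated figure of over 80%.
- 475 v 95: SE = 0.03216, power 87.5%.

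**The survey.** 79 − 47 = 32, and 32/79 = 40.5% (exact 95% CI 29.6% to 52.1%) were in hospital for under 4 days. A stay of under 4 days cannot contain 5 days of inpatient IV treatment.

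**Effect of early switching on the ITT test.** Put the true rates at the margin: 9% on completed 5-day IV and 19% on step-down. The IV group's ITT rate becomes 0.09 + 0.10ch, and the ITT difference becomes d = 0.10 − 0.10ch. The chance of declaring non-inferiority is Φ((0.10 − d)/SE − 1.96), with 475 v 95.

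| c | h = 1 (full risk) | h = 0.5 |
|---|---|---|
| 0 | 2.5% | 2.5% |
| 10% | 4.7% | 3.5% |
| 20% | 7.8% | 4.7% |

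Example for c = 10%, h = 1: the IV rate is 0.10, d = 0.09, SE = √(0.10 × 0.90/95 + 0.19 × 0.81/475) = 0.03566, and Φ(0.280 − 1.96) = 4.7%. Simulating the Wald interval directly at h = 1 gives 1.5%, 3.1% and 5.8% for c = 0, 10% and 20%: somewhat lower, with the same pattern.

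**Cost of requiring the weighted analysis.** As a rough guide, let only the 95(1 − c) adherent IV children carry information, against 475 on step-down, with 9% failure in both.
- c = 10%: 85.5 children, SE = 0.0336, power about 84%.
- c = 20%: 76 children, SE = 0.0354, power about 81%.
- c = 40%: 57 children, SE = 0.0401, power about 70%.

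Variable weights would reduce these further.

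**The case against.** The case on the other side is substantial.

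- **The analysis is not ITT alone.** Section 9.5 plans weighting for exactly these deviations, and 9.3.1 makes change from the allocated regimen a separate outcome on which interpretation is to be conditional. A reader might infer that non-adherence is ignored, and the protocol does not support that. What stands is that the weighted analysis is secondary and nothing in the protocol requires it to agree before non-inferiority is concluded.
- **Section 9.5 is a summary, and an agreement rule could sit in the SAP.** This is fair, so the absence of such a rule is not by itself a fault. The point rests on what the protocol does state: an unsupported adherence conclusion, together with ITT as the primary population for a powered non-inferiority comparison.
- **The survey is not a forecast.** It records hospital stay in routine care, not IV duration or in-trial adherence, and it took children up to 10 years. Section 1.4.2 cites the same section for a modal IV duration of 4–5 days in several sites. The trial adds safeguards: parents must accept 5 days IV (3.1, criterion 7), children stay in hospital throughout with travel costs paid (5.2.1), and the trial pays for hospitalisation where it is not free (9.2.4). A reader might take 41% as the expected switching rate. That is not supported; it shows pressure only.
- **The 8% without oral antibiotics does not mean 92% contamination.** That count covers any length of stay. Oral drugs after a completed IV course lengthen treatment in the IV group and do not bias towards non-inferiority. This objection stands in full, and the argument here concerns early switching or discharge only.
- **ITT suits a pragmatic strategy trial.** That is so, but the dilution still acts in the favourable direction for a non-inferiority claim.

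**Conclusion.** The adherence conclusion in 5.2.3 is not supported by its stated reason, and it sits badly, as does the expectation in 5.2.1, with the survey in 1.4.4. Early switching in the IV group would bias the ITT-primary comparison towards non-inferiority. The inflation is moderate over a plausible range: from 2.5% to about 5% at 10% switching and 8% at 20% with full crossover of risk, or 3.5% and 4.7% with half. These figures assume true failure of 9% v 19% and 475 v 95 evaluable children. The switching fraction is an assumption throughout.

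A reader might go further and expect inflation of 12% to 18%. The same formula gives that only at 30% to 40% switching with full crossover, and nothing in the protocol supports such a rate under trial conditions. Children who switch late, after several days of IV, are only partial crossovers.

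**What to change.** 1. In 9.5, unless the SAP already does so, state that non-inferiority to 5-day IV is claimed only if the ITT analysis and the planned inverse-probability-weighted analysis both exclude the 10% margin. For the IV group, the weighting should address children switched to oral treatment or discharged before completing 5 days, and not oral antibiotics given after completion.
2. Reconcile 1.4.4, 5.2.1 and 5.2.3. Limit the 5.2.3 statement to missed doses and acknowledge early switching as a separate risk. Do not write the survey percentages in as expected trial non-adherence.
3. Report the share of the IV group completing 5 days of IV, by site, to the DMC.

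No new data are needed: antibiotics received and reasons for change are already collected (5.8 and 6.6). The cost is a harder claim. Approximate power falls from 87.5% to 84% at 10% switching, 81% at 20% and 70% at 40%, before any further loss from variable weights.

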5.3 ORAL AMOXICILLIN AND CO-AMOXICLAV

5.3.1 PRODUCTS & TREATMENT SCHEDULE

Children randomised to oral amoxicillin or co-amoxiclav will be provided with dispersible tablets as trial supplies to be prepared and given orally twice daily by the ward nurses whilst still in hospital and by the parent/carer of the child after discharge, following instructions from the study staff. Medication must be taken as dispersed tablets and not swallowed whole, divided, or crushed. Dosing will be by weight band as shown in [Body weight](#) should be obtained by ward nurses, using standard methods (as to determine the doses of intravenous antibiotics). Body weight reported by parents is not acceptable. Additionally, body weight should be measured on the day of switch to oral antibiotic to assign the child to the correct weight-band dosing schedule, as weight may change considerably since admission (e.g. if the child was dehydrated at the time of enrolment into the study).

5.3.1.A Criteria for Moving from Intravenous to Oral Antibiotics

The main criteria for moving from intravenous to oral antibiotics is that the child should have improved clinically, be currently clinically stable or continuing to improve, and be well enough to take medication by mouth, i.e. can ingest and keep down the dispersible tablets when made up in a small amount of liquid, and hence oral absorption of the antibiotic is likely to be good. Children may move to oral medication whilst inpatients (e.g. if they are still receiving supplemental oxygen). See MOP for further details.

Children should be discharged on oral medication as soon as they are clinically stable and have received and retained at least one dose of oral antibiotics. See MOP for further details.

Table 7.

Body weight should be obtained by ward nurses, using standard methods (as to determine the doses of intravenous antibiotics). Body weight reported by parents is not acceptable. Additionally, body weight should be measured on the day of switch to oral antibiotic to assign the child to the correct weight-band dosing schedule, as weight may change considerably since admission (e.g. if the child was dehydrated at the time of enrolment into the study).

5.3.1.B Criteria for Moving from Intravenous to Oral Antibiotics

The main criteria for moving from intravenous to oral antibiotics is that the child should have improved clinically, be currently clinically stable or continuing to improve, and be well enough to take medication by mouth, i.e. can ingest and keep down the dispersible tablets when made up in a small amount of liquid, and hence oral absorption of the antibiotic is likely to be good. Children may move to oral medication whilst inpatients (e.g. if they are still receiving supplemental oxygen). See MOP for further details.

Children should be discharged on oral medication as soon as they are clinically stable and have received and retained at least one dose of oral antibiotics. See MOP for further details.

Table 7: Dosing for oral amoxicillin and co-amoxiclav

FORMULATION	WEIGHT BAND	# TABLETS AM	# TABLETS PM	# TABLETS DAILY	DAILY DOSE (MG)
Amoxicillin (250mg tablets)	3 - <6kg	1	1	2	500
	6 - <10kg	2	1	3	750
	10 - <14kg	2	2	4	1000
	14 - <20kg	3	3	6	1500
	20 - <25kg	4	4	8	2100
	25 - <35kg	5	5	10	2500
Co-amoxiclav 7:1 (200/28.5mg tablets)	3 - <6kg	1	1	2	400/57
	6 - <10kg	2	2	4	800/114
	10 - <14kg	3	2	5	1000/142.5
	14 - <20kg	4	4	8	1600/228
	20 - <25kg	5	5	10	2000/285
	25 - <35kg	6	6	12	2400/342
Co-amoxiclav 4:1 (250/62.5mg)	3 - <6kg	1	1	2	500/125
	6 - <10kg	2	1	3	750/187.5
	10 - <14kg	2	2	4	1000/250
	14 - <20kg	3	3	6	1500/375
	20 - <25kg	4	4	8	2000/500
	25 - <35kg	5	5	10	2500/625
Co-amoxiclav 14:1 (150/10.725mg)	3 - <6kg	2	1	3	450/32.175
	6 - <10kg	3	2	5	750/53.625
	10 - <14kg	4	3	7	1050/75.075
	14 - <20kg	5	5	10	1500/107.25
	20 - <25kg	7	6	13	1950/139.425
	25 - <35kg	8	8	16	2400/171.6

Note: inclusion criteria include weights up to 30kg ([Section 3](#)), but dosing table includes weights up to 35kg to allow for dehydrated children gaining weight during admission, and to align with WHO HIV weight-bands.

